This task identifies brain areas involved in processing rewards and expected values. [54,55]. The task is divided into two, 48 trial, 7-minute scanner runs (Figure 2). On each trial, participants virtually “bet” via button press whether the number on the next card displayed (range=1-9) will be higher or lower than 5 (guess (?) phase). Next, an expectancy card is shown communicating the likelihood that the bet will result in a win, a loss, no change, or win/loss equally likely (cue phase). The number is then shown (# phase), followed by the win/loss amount (feedback phase). Expectancy cues are accurate on 50% of trials (except for neutral trials) producing neural “prediction errors” on misleading cue trials. Trials are separated by a 0.5-1.5s jittered inter-trial interval. Trial order is randomized with 12 trials per category (win, loss, neutral, ambiguous).

[figure not shown]

Fig. 2 The reward expectancy card guessing task⁵⁴ On each trial, participants guess (?) whether the number on a later card (#) is higher or lower than 5. An intervening cue card (Cue) sets an outcome expectancy. Feedback (\$) after the card reveal corresponds to wins, losses, or a push. The difference between the actual outcome - win, loss, or push ("\$") - and the expected value is the prediction error.

III. Stop-signal reaction time task (SSRT)

The SSRT measures inhibitory cognitive control [57,58] The task is divided into two, 128 trial scanner runs. On each trial, participants indicate whether a visually-presented ‘go’ arrow stimulus points to the left or right (50/50% probability) using a MRI-safe button box. During 25% of trials (random assignment), a stop-signal (up arrow) indicating that responses are to be withheld is delivered at a delay after the go arrow. On stop trials, the delay between the go cue and the stop signal is the ‘stop-signal delay’ (SSD). The SSD is varied based on performance[58]. Null events ranging from 0.5 and 4 s (mean, 1 s) will be interspersed between trials.

D4.4 Intervention [(active or sham) TMS +BCBT]

If eligible and willing to participate in the intervention, participants will be scheduled for the start of TMS+BCBT as soon as scheduling allows following the baseline visit and following their first MRI visit (if applicable). However, for

participants who are scheduled to start the intervention phase more than 2 weeks after the baseline visit, the C-SSRS, IDSSR, and PCL-5 will be readministered within 1 week prior to start of intervention.

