Differences in white matter integrity between groups. PFC regions involved in cognitive control are anatomically connected to striatum by white matter pathways, e.g. the cortico- striato-thalamic loops². Damage to these pathways may undermine efficient neurotransmission of top-down cognitive control signals which are fundamental for goal- directed behaviors including decision-making⁵. In individuals with STBs, efficiency of the cognitive control system may permit the development of more deliberate suicidal behaviors rather than impulsive attempts. Deterministic tractography statistics will be contrasted between groups to test this hypothesis. Tractography procedures match those used above (*Differences in white matter integrity between Veterans with STBs and controls*). Subjects' track statistics (anisotropy, track density) will be entered into GLMs contrasting high-risk and low-risk Veterans with STBs.

Univariate fMRI differences in inhibitory control. This analysis tests the hypothesis that response inhibition, a component of cognitive control, will be superior in high-risk Veterans relative to their lower-risk Veterans and controls. We anticipate that the fMRI signal in VLPFC during successful inhibition will be strongest in the high-risk group relative to lower-risk Veterans with STBs and controls.

Preprocessed SSRT will be entered into subject-level fixed-effect GLMs constructed with SPM12. Regressors for the following trial types will be constructed: Go trials, Stop Inhibit trials, Stop Respond trials, along with two nuisance regressors (go errors, non- response trials). Stop-Inhibit and Stop Respond trials represent successful, and unsuccessful attempts to halt responses in progress. Null events constitute an implicit baseline. GLMs will be created by convolution of the canonical hemodynamic response function with model regressors. Motion estimates and mean signal in cerebrospinal fluid will also be included as nuisance regressors. Contrasts for each trial type and Stop Inhibit- Stop Respond trials will be included in first-level models. Second-level models where subjects are treated as random effects will be estimated by regressing first-level contrast betas against group. Averaged betas across voxels from ROIs will also be extracted from each subject and contrasted between groups to conduct ROI-level hypothesis tests.

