Adaptive decision-making and inhibitory control. Here, we will test the hypothesis that high-risk Veterans' superior capacity for inhibitory cognitive control enables less impulsive decision-making. Separate GLMs will be constructed predicting either delay discounting (Monetary-Choice Questionnaire), or the proportion of risky choices (Iowa Gambling Task). Predictor variables include Group (high-risk, low-risk, controls) and Inhibitory Control (stop signal reaction time), Impulsivity (BIS-11 or alternatively, UPPS scores), or fMRI activation during correct inhibit SSRT trials. Follow-up control analyses in which the performance metrics from the Dimensional Card Sort and Flanker Tasks (see Research Plan

- Methods and measures) are substituted for the Inhibitory Control measure will be conducted to determine if risk is specifically related to inhibitory control or is a by-product of generally better cognitive control.

Resting-state functional connectivity in the cognitive control network and its relationship to decision-making. Greater functional cohesion amongst ROIs in cognitive control networks is associated with better cognitive control performance ⁶². Greater activation in cognitive control regions is also associated with decisions that promote long-term goals [92]. Thus, correlations between cognitive control ROIs may be stronger in high-risk suicidal Veterans given that their better decision-making performance may be due in part, to superior cognitive control. Functional connectivity analyses will be conducted using the CONN Toolbox and according to methods outlined in D9. The GLM testing logic follows the sequence above in Analysis D10.5.5, however, beta values describing functional connectivity amongst ROIs in the control network

for each subject will be used to predict Monetary Choice and Gambling performance.

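### The stop-signal fMRI test of response inhibition names no test contrast and omits Stop Inhibit minus Go, the one that would remove the response common to all trials

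*Combined protocol and SAP*

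**What the plan says.** The analysis is in E3.2, under the paragraph on univariate fMRI differences in inhibitory control. The aim is explicit: "This analysis tests the hypothesis that response inhibition, a component of cognitive control, will be superior in high-risk Veterans", relative to lower-risk Veterans and controls. So is the predicted signal: "We anticipate that the fMRI signal in VLPFC during successful inhibition will be strongest in the high-risk group".

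The first-level model is also clear. "Regressors for the following trial types will be constructed: Go trials, Stop Inhibit trials, Stop Respond trials", with two nuisance regressors for go errors and non-responses. The two stop-trial types are defined by outcome: "Stop-Inhibit and Stop Respond trials represent successful, and unsuccessful attempts to halt responses in progress". The reference for single-condition estimates is given as "Null events constitute an implicit baseline", and the task description in D4.3.4e (item III) adds "Null events ranging from 0.5 and 4 s (mean, 1 s) will be interspersed between trials".

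The contrasts are then listed: "Contrasts for each trial type and Stop Inhibit- Stop Respond trials will be included in first-level models". Their betas go to the group models, and ROI averages are compared between groups. The paragraph does not say which contrast decides the VLPFC hypothesis. Stop Inhibit minus Go is not named there or anywhere else in the document.

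The next paragraph of E3.2, on adaptive decision-making, uses "fMRI activation during correct inhibit SSRT trials" as one possible predictor of delay discounting and risky choice, without saying which contrast supplies it.

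**The concern.** By the task description, a stop signal follows a go arrow after a delay, so each stop trial begins as a go trial. The response to a successful stop measured against null events therefore contains arrow perception, choice, response preparation and general task engagement as well as stopping. A group that responds more to every trial would show a larger value with no difference in inhibition.

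The only difference contrast listed compares two trial types that both carry a stop signal and an attempt to stop. Whatever stopping activity is equal on the two is subtracted out. What remains includes the button press and the error response, which occur only on failed stops.

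At stake is the meaning of a positive or null VLPFC result. E3.2 says it wants to know whether the link with suicide risk is specific to inhibitory control, and a non-specific activation measure weakens that claim. With no contrast named as the test, the choice can also be made after the results are seen.

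**Working it through.** The documents give no figure for this analysis, so there is none to reproduce.

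**Inputs from the documents.** Two runs of 128 trials, 25% of them stop trials (D4.3.4e): 256 trials, 64 stop and 192 go. High-risk and low-risk groups of up to 30 each (E3.2, participant groups). Two-tailed .05 with Bonferroni over ROIs (E3.2, MRI analyses).

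**Assumptions.** The number of ROI comparisons is not stated. I take 7: three VLPFC parts, DLPFC, two ACC parts, striatum. The stop success rate is not stated. I take 50%, range 40% to 60%. The size of any general group difference is unknown. I take 0.3, 0.5 and 0.8 SD.

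**Step 1: what each contrast contains.** Let V be the response common to all trials, M the button press, S the stopping process, A the salience of the infrequent stop signal, and E the error response.

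- Go = V + M
- Stop Inhibit = V + S + A
- Stop Respond = V + M + S + A + E

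Then:

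- Stop Inhibit v null events = V + S + A. V stays in.
- Stop Inhibit minus Stop Respond = −(M + E) if S is equal on both. If S differs by outcome, that difference is added.
- Stop Inhibit minus Go = S + A − M. V cancels and S stays.

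**Step 2: how often a general difference looks like inhibition.** Suppose the groups differ only in V, by d SD of the Stop Inhibit beta. For a two-sample t test with 30 per group, df = 58 and the noncentrality is d × √(30/2):

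| d | Noncentrality | Significant at .05 (critical t 2.002) | Significant at .05/7 (critical t 2.789) |
|---|---|---|---|
| 0.3 | 1.162 | 21% | 6% |
| 0.5 | 1.936 | 48% | 21% |
| 0.8 | 3.098 | 86% | 62% |

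An additive V cancels in Stop Inhibit minus Go, which stays at its nominal level.

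**Step 3: behaviour under other differences.** Illustrative simulation: 4,000 replicates, 30 v 30, uncorrected .05. The five components are independent with SD 1, measurement noise has SD 0.25 (Go) or 0.6 (stop trials), and one component is shifted by 1 SD. All these values are assumed. Rejection rates:

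| Groups differ only in | Stop Inhibit v null | Stop Inhibit − Stop Respond | Stop Inhibit − Go |
|---|---|---|---|
| General response (V) | 0.55 | 0.05 | 0.05 |
| Stopping, equal on all stop trials (S) | 0.55 | 0.05 | 0.54 |
| Stop-signal salience (A) | 0.55 | 0.05 | 0.54 |
| Motor response (M) | 0.05 | 0.63 | 0.54 |
| Error response (E) | 0.05 | 0.64 | 0.05 |
| Nothing | 0.05 | 0.05 | 0.04 |

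**Step 4: estimability and scan-noise precision.** In 200 simulated HRF-convolved designs the three regressors had full rank, so Stop Inhibit minus Go is estimable. On trial counts the variance factor is 1/n₁ + 1/n₂. At 50% success:

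- Stop Inhibit minus Stop Respond: 1/32 + 1/32 = 0.0625
- Stop Inhibit minus Go: 1/32 + 1/192 = 0.0365
- SE ratio: √(0.0365/0.0625) = 0.76

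The ratio is 0.82 at 40% success and 0.69 at 60%. The convolved designs also gave 0.76 at 50%. This is scan noise within a subject. Group tests also carry between-subject variance, so it is not a ratio of group-level precision.

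**The case against.** The strongest reply is that the planned set, read together, already guards against the artefact. Go against baseline is one of the listed contrasts and goes to the group level, so a general response difference should show there. That same difference leaves Stop Inhibit minus Stop Respond at its nominal rate. This stands. A reader might infer that the plan will report superior inhibition whenever one group simply responds more. The document does not support that, because it nowhere says that Stop Inhibit against null events alone decides the hypothesis. The defect is that no contrast is named as the test.

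A reader might also infer that Stop Inhibit minus Stop Respond cannot detect inhibition at all. That holds only if stopping is recruited equally on successful and failed stops, which the document does not establish. The prediction concerns successful inhibition, so success against failure is a relevant comparison and worth keeping.

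Nor does Stop Inhibit minus Go isolate inhibition. It responds to salience and motor differences about as often as to stopping (0.54 in each case). It also removes only an additive general response: a multiplicative gain in BOLD, as vascular reactivity might produce, scales the difference and does not cancel.

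Two further limits stand. The 48% figure uses uncorrected .05 and one assumed effect size, whereas the plan corrects over ROIs. The illustration also covers one pair of groups, while the hypothesis places high-risk Veterans above both low-risk Veterans and controls. Imaging is not the only evidence either: E3.2 compares behavioral stop-signal data and plans Card Sort and Flanker analyses to check specificity.

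That Stop Inhibit minus Go could be formed later from saved betas is true, but it does not answer the lack of a prior commitment.

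**Conclusion.** The concern holds in a limited form. E3.2 tests an inhibition hypothesis without naming the deciding contrast, and its list omits the one that removes the response common to all trials while retaining stopping.

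The size depends on an unknown general group difference. Across 0.3 to 0.8 SD, Stop Inhibit against null events would be significant without any inhibition difference in 21% to 86% of studies at .05, or 6% to 62% with correction over an assumed 7 ROIs. These are illustrations for 30 v 30, not estimates of what the trial will find.

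The reach is one Aim 2 imaging hypothesis and, because its contrast is unstated, the activation predictor in the decision-making models. Section A5 places baseline brain-behavior differences between suicidal Veterans and controls among the exploratory hypotheses. The trial's primary outcome is unaffected.

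**What to change.** In the E3.2 paragraph on univariate inhibitory-control differences:

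1. Add Stop Inhibit minus Go to the first-level contrasts and name it in advance as the ROI contrast for the VLPFC hypothesis.
2. Keep Stop Inhibit minus Stop Respond as a complementary contrast on success against failure.
3. State that both will be read beside the already planned group result for Go against baseline and the behavioral stop-signal reaction time.

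In the paragraph on adaptive decision-making, state that the fMRI activation predictor uses the same Stop Inhibit minus Go contrast.

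The cost is one contrast vector and a few sentences, with no new data or scan time. The write-up should acknowledge what the new contrast still carries: detection of an infrequent signal, the absent button press, and any multiplicative difference in BOLD response.

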Rationale: Studies comparing decision-making between individuals who have made high-risk (well-organized, highly lethal) attempts vs. those making less organized or less medically serious attempts have found that decision-making is less impulsive in higher- risk attempters [86]. In fact, decision-making in high-risk attempters is even less impulsive than it is in healthy controls. Some propose that the capacity to make a serious suicide attempt develops alongside the ability to inhibit prepotent pain and fear responses associated with death [87]. Thus, paradoxically, greater inhibitory cognitive control may facilitate development of suicidal behavior. As a test of this hypothesis, we will compare behavioral and functional neuroimaging data collected during the SSRT, an inhibitory cognitive control task, between high- and lower-risk Veterans with STBs. We will also examine associations between suicide and other cognitive control measures to assess the specificity of the link between attempts and inhibitory control. to assess the specificity of the link between attempts and inhibitory control.

Participant groups: The high-risk group will be comprised of Veterans with history of suicide attempt (up to n=30), while the low-risk group will include Veterans with ideation only (up to n=30). See alternative methods for risk grouping in the Design Considerations section below. Diagnosis matched controls (up to n=60) are also used in some analyses.

Data sources: Structural data (cortical thickness and volume) and diffusion MRI data. FMRI data used in Aim 2 analyses will come from either the SSRT, the scanned decision-making task, or resting state runs. Behavioral measures of decision-making include data from the scanned decision-making task. Behavioral measures of cognitive control include data from the scanned SSRT, and the un-scanned Intra-Dimensional Card Sort and Flanker tasks.

General statistical details: Age and sex will be treated as covariates of no interest in all statistical analyses. Intracranial volume (computed by Freesurfer) will also be used as a nuisance covariate in morphometry analyses to control for size-related variance. Residual effects of motion on functional connectivity estimates will be tested post hoc by regressing individuals' frame-to- frame motion against functional connectivity beta values ⁵⁵. Potential effects of impulsivity, depression, anxiety, and sleep on outcomes will be explored in post hoc sensitivity analyses.

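### E3.2 states an indirect-path hypothesis (risk group to inhibition to choice), but neither term of the named GLM tests that path, and no rule ties its conclusion to the separate group comparison of inhibition

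*Combined protocol and SAP*

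**What the plan says.** The paragraph of E3.2 on adaptive decision-making and inhibitory control gives the hypothesis as high-risk Veterans' "superior capacity for inhibitory cognitive control enables less impulsive decision-making". The outcomes come next: "Separate GLMs will be constructed predicting either delay discounting (Monetary-Choice Questionnaire), or the proportion of risky choices (Iowa Gambling Task"). Then the model terms: "Predictor variables include Group (high-risk, low-risk, controls) and Inhibitory Control (stop signal reaction time"), with impulsivity scores or stop-signal activation as further or substitute predictors. Follow-up models swap card-sort and flanker scores in for the inhibition measure "to determine if risk is specifically related to inhibitory control or is a by-product of generally better cognitive control".

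The paragraph names no indirect effect, no deciding coefficient and no decision rule. The resting-state paragraph after it says its testing logic follows an earlier analysis. The section number it cites (D10.5.5) does not exist in this document, but the context points to the same GLM.

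Two other places in E3.2 bear on the first link. The Rationale says that "we will compare behavioral and functional neuroimaging data collected during the SSRT" between high- and lower-risk Veterans. The univariate fMRI paragraph tests whether "response inhibition, a component of cognitive control, will be superior in high-risk Veterans" relative to lower-risk Veterans and controls. The groups are "Veterans with history of suicide attempt (up to n=30"), "Veterans with ideation only (up to n=30"), and up to 60 matched controls in some analyses. Age and sex are covariates throughout.

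**The concern.** The hypothesis is a chain. It needs high-risk Veterans to differ from low-risk Veterans in inhibition, and it needs inhibition to relate to choice.

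Once Group is in the model, the inhibition coefficient compares people within the same group. It can be large when all three groups have identical inhibition. The Group coefficient is the part of the group difference that inhibition does not account for; if the hypothesis were fully true, it would be near zero. So the model's two kinds of term answer two other questions.

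The follow-up swaps show the same mismatch. They are meant to say whether risk relates specifically to inhibition, yet risk is a predictor in that model and no coefficient from risk to inhibition is estimated.

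At stake is a mechanistic statement about suicide attempters that could be reported on the strength of an ordinary association between inhibition and discounting. Half of the planned sample (60 of 120) is non-suicidal controls, who can contribute much of that association.

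**Working it through.** **The plan's own figure.** The only power statement for this aim is in E3.1 (paragraph numbered E5.1): 85% power, group effect f = 0.4, three groups, two covariates, N = 72. Noncentral F with df1 = 2, df2 = 72 − 3 − 2 = 67 and noncentrality 72 × 0.4² = 11.52 gives power 0.853, and 72 is the smallest N reaching 0.85. It reproduces. It concerns a group main effect at 24 per group and says nothing about the GLM examined here.

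**Inputs.** Groups 30/30/60 and covariates age and sex are from E3.2. Two-sided 0.05 is stated there for region-of-interest analyses and assumed here for the behavioral GLM. The within-group correlation r between inhibition and choice is not in the documents; 0.2 to 0.4 is assumed, with other cases shown.

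**What each term estimates.** With M = inhibition and Y = discounting or risky choice:
- M = a·High + controls + age + sex + error
- Y = c′·High + b·M + controls + age + sex + error

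The hypothesis concerns a × b. The GLM reports b and c′. Neither contains a.

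**Closed-form check with a = 0.** The residual degrees of freedom for M given group, age and sex are 120 − 5 = 115, so the noncentrality of the b test is about r√115/√(1 − r²), against a critical value of 1.98.
- r = 0.2: 0.204 × 10.72 = 2.19; power ≈ Φ(0.21) = 58%.
- r = 0.3: 0.314 × 10.72 = 3.37; power ≈ Φ(1.39) = 92%.

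**Simulation with no group difference in inhibition** (4,000 trials per row):

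| Within-group correlation | Inhibition term significant | High v low contrast in inhibition significant | Both significant |
|---|---|---|---|
| 0 | 4.7% | 5.1% | 0.2% |
| 0.2, all groups | 59% | 4.4% | 2.4% |
| 0.3, all groups | 91% | 4.6% | 4.3% |
| 0.4, all groups | 99.6% | 4.9% | 4.9% |
| 0.3, controls only | 38% | 5.1% | 2.1% |
| 0.5, controls only | 78% | 4.9% | 3.7% |

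**Percentile bootstrap interval for a × b** (1,500 trials, 500 resamples each), same null: 2.3% at r = 0.2, 5.2% at r = 0.3, 6.3% at r = 0.4, and 2.1% with r = 0.3 in controls only. The Monte Carlo standard error is about 0.6 points near 5%. Another simulation of this interval gave 2 to 4%.

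**A Group-by-inhibition term would not repair it.** With a true indirect path (a = 0.5 SD, r = 0.3), the interaction test rejects in 4.9% of trials, because it asks whether slopes differ between groups. The adjusted Group contrast rejects in 5.3%.

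**Power of a test of the path.** The 30 v 30 contrast in inhibition limits it: 49% at 0.5 SD and 87% at 0.8 SD. Multiplying by about 91% for the second link at r = 0.3 gives 0.49 × 0.91 = 45% and 0.87 × 0.91 = 79%. Simulation agrees: 42 to 48% and about 78%.

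**The case against.** The strongest reply is that this judges one model in isolation. E3.2 does compare stop-signal behavior and activation between risk groups, so the first link is examined. A careful report would notice if that contrast were null while the GLM's inhibition term was significant. This stands, and it narrows the problem. It does not remove it, because no sentence makes the conclusion conditional on that contrast.

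Second, E3.1 plans group comparisons of discounting and gambling. In linear models on the same people and covariates, the change in the Group coefficient after adding inhibition equals the product a × b. E2.4 names that before-and-after comparison, but for treatment effects in Aim 1 only, and without an interval specified for it. The ingredients are present; the test is not.

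Third, a reader might infer that the plan carries a 60 to 90% false-claim rate. The documents do not support that. They never say that the inhibition coefficient alone decides the hypothesis, and the predictor list is introduced as inclusive, so it may not be complete. The 60 to 90% is the power to detect a real, assumed association; it becomes an error rate only if that association is read as support for the full chain.

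Fourth, a reader might infer that any correlation, in any group, makes the term significant. It does not: 59% at r = 0.2 in all groups, and 38% at r = 0.3 in controls only.

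Finally, this hypothesis is not among the primary or secondary hypotheses in A2 and A3, and A5 labels the baseline brain-behavior hypotheses exploratory.

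**Conclusion.** The point holds as a gap between hypothesis and test. The GLM named in E3.2 cannot by itself support the statement that high-risk Veterans' better inhibition leads to less impulsive choice. The plan does not say how its result is to be combined with the separate group comparison of inhibition.

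If the inhibition term were taken as support, a true null on the first link would still yield a significant result in about 60% (r = 0.2) to 90% (r = 0.3) of trials at 30/30/60, and in about 38% if r = 0.3 holds in controls only. Requiring both links brings this to between 2 and 5%. These figures rest on assumed correlations, the maximum planned group sizes, normal errors and two-sided 0.05. The structural point, that neither coefficient contains the group difference in inhibition, rests on none of them.

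The same gap probably affects the resting-state analysis, but its broken cross-reference prevents certainty. The matter is worth correcting because it is cheap. It changes no primary outcome, treatment comparison or sample size.

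**What to change.** In the E3.2 paragraph on adaptive decision-making and inhibitory control:

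- Estimate the high- versus low-risk indirect effect through stop-signal reaction time, separately for discounting and for risky choice. Use the product of the group-to-inhibition and inhibition-to-choice coefficients, adjusted for age and sex, with a percentile bootstrap 95% interval that resamples participants. Claim support only if the interval excludes zero in the hypothesized direction.
- At minimum, state that the claim requires both a significant high- versus low-risk stop-signal contrast and a significant inhibition term.
- Name stop-signal reaction time as the main intermediate, and treat activation and connectivity as supportive. Say whether support on either outcome suffices or both are needed.
- Report the present inhibition coefficient as a general association. Apply the same path logic to the card-sort and flanker substitutions.
- Replace the causal verb with wording such as *is consistent with*, since group, inhibition and choice are cross-sectional here.
- Correct the section reference in the resting-state paragraph.

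The cost is a few sentences and a few lines of code on the same data. The drawback is fewer positive findings: power is about 42 to 48% at a 0.5 SD group difference and about 78% at 0.8 SD, with r = 0.3. That limit comes from comparing 30 with 30, and the plan should say so.
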